3.3 Preclinical evidence

See Chapter 3.1 above.

3.4 Current clinical evidence

To the knowledge of the authors, there are currently no studies that have investigated apparatus-based, passive continuous mobilization in the caudal / cranial direction of the patella. The majority of existing studies are limited to the effect of manual therapy interventions (see 3.1 Background and Rationale below).

3.5 Medical product: method of application in the study

As part of this clinical study, the displacement of the patella in the caudal / cranial direction by the Patello device will be recorded and quantified. This is to prove the effectiveness of this device. For more detailed specifications, see Chapter 3.2 Medical Device and Indication.

3.6 Intervention Patello

In order to record a possible positive effect of repetitive mobilization, the measurements are carried out several times: after the positioning of the device (1st measurement, pre-mobilization), after 1 mobilization, after 10 mobilizations, after 20 mobilizations, after 30 mobilizations and after 50 mobilizations (2nd to 6th measurement). The measurements are carried out on 2 days, with a 2-day

SUPSI

break in between. The settings are redefined per measurement day, but are maintained during measurements 1-6 to guarantee comparability.

The exact procedure for the measurements can be seen in Chapter 9.2.

Randomization

The allocation of the application page will be randomly assigned by lot.

3.7 Risk / Benefits

The possible occurrence of risks from the use of the Patello is to be assessed as small: short-term skin irritations and/or paraesthesia could occur.

The subjects do not benefit from participating in the study. The study serves to prove the effectiveness of the Patello device. If this is the case, the device can be used in the rehabilitation process of patients with the above-mentioned knee joint problems.

Justification of the choice of population

This series of studies will be conducted with healthy adults to assess the extent of the Quantify displacement of the kneecap by means of the patello.

Table 1: Overview of inclusion and exclusion criteria

Inclusion Criteria	Exclusion criteria

- Adults aged 18 to 30 Years- No surgical interventions and/or current complaints (pain at rest or during exertion) on the musculoskeletal apparatus in the area of the lower extremities- closed, intact skin conditions in the knee and thigh area- Don't be afraid of the intervention	
- Adolescents and adults over 30 years of age- Surgical interventions and/or current complaints (pain at rest or during exertion) on the musculoskeletal Apparatus in the area of the lower extremities- no closed, intact Skin conditions in the knee and thigh area- Fear of intervention

The test subjects are comprehensively informed about the course of the study and possible risks before they are accepted to participate in the study. You will also receive the information in written form and have the opportunity to ask questions if anything is unclear. The declaration of consent explains to them what their rights and obligations are when participating. In addition, they are informed that they may withdraw from participation at any time without giving reasons, without incurring any disadvantages as a result.

4 STUDY OBJECTIVES

SUPSI

4.1 General objectives

The aim of this study is to measure the effectiveness of the Patello device. It is designed to move the patella on its plain bearing in the caudal / cranial direction, passively and continuously. However, it is still unclear whether and to what extent the displacement of the patella is effective.

4.2 Primary objectives

A primary and secondary outcome was defined as the primary goal. The primary outcome, the displacement of the patella, detected by an imaging ultrasound device (esaote MyLabClassicC, Genoa, Italy, www.esaote.com) and evaluated by a dedicated software (OsiriX, www.osirix-viewer.com), is represented in mm and is considered an objective parameter.

The secondary outcome, the recording of the subjective well-being of the test person, is determined using a visual analogue scale (VAS scale 0-10) and reflected in the number of cm. It is considered a subjective parameter.

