5 STUDY OUTCOMES

5.1 Primary outcomes

A primary and secondary outcome was defined as the primary goal. The primary outcome, the displacement of the patella, detected by an imaging ultrasound device (esaote MyLabClassicC, Genoa, Italy, www.esaote.com) and evaluated by a dedicated software (OsiriX, www.osirix-viewer.com), is represented in mm and is considered an objective parameter.

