5.2 Secondary outcomes

Subjective information on general well-being

The secondary outcome, the recording of the subjective well-being of the test person, is determined using a visual analogue scale (VAS scale 0 - 10) and reflected in the number of cm. The value "0" describes "maximum feeling of well-being", the value "10" a "maximum feeling of discomfort". The value is considered a subjective parameter.

Security considerations

SUPSI

No further results are recorded that would serve safety.

Discontinuation of the experiment is the responsibility of the examiner with regard to the subject's subjective feelings and expressions.

If a test subject does not feel comfortable during the intervention according to his or her subjective assessments, he or she can discontinue the experiment and withdraw participation in the study without any disadvantages.

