10 STATISTICAL METHODS

10.1 Hypotheses & Factors

Mobilization of the patella in the caudal / cranial direction by the patello – repetitive mobilizations versus one-time mobilization Objective displacement of the patella:

H0 The patella does not shift significantly more during repetitive mobilizations than during a single mobilization by the patello.

H1 The patella shifts significantly more during repetitive mobilizations than during a single mobilization by the patello.

Subjective well-being of the subject:

H0 Subjective well-being does not change significantly more with repetitive mobilizations than with a single mobilization by the patello.

H1 Subjective well-being changes significantly more with repetitive mobilizations than with a single mobilization by the patello.

A 2-factor analysis is carried out.

Factor 1: Intervention

Factor 2: Time intervention: Start (pre-intervention, 1st measurement), after a single mobilization (2nd measurement), after 10 (3rd measurement), after 20 (4th measurement), after 30 (5th measurement), after 50 mobilizations (6th measurement)

Sample size

The planned sample size is $n = 30$ subjects. This size is expedient, time-wise and financially feasible for the study.

10.2 Criteria for the statistical use of data in the case of incomplete data sets

A complete mobilization interval must be completed for the data to be included in the study. If a mobilisation interval (e.g. interval '20 mobilisations', but termination after 15 mobilisations) has to be interrupted, only the previously collected complete mobilisation interval data can be used. This ensures that all data remains homogeneous and comparable. No substitute is sought for the missing mobilization interval data.

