10.3.2 Primary Analysis

The statistical data analysis is carried out by the statistician after completion of the data collection of the entire project.

Repeated measures analysis of variance (MANOVA) A 2-factor analysis is performed.

Factor 1: Intervention

Factor 2: Time intervention: Start (pre-intervention, 1st measurement), after a single mobilization (2nd measurement), after 10 (3rd measurement), after 20 (4th measurement), after 30 (5th measurement), after 50 mobilizations (6th measurement)

The significance level is set at $P < 0.05$, and the statistical data analysis is carried out with SPSS V. 24.

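### Sections 4.2, 5.1 and 10: two outcomes share the primary goal, but no testing order, adjustment or named repetitive-versus-single contrast is given; a cheap wording fix settles it

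*Combined protocol and SAP*

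**What the plan says.** Section 4.2, headed as the primary objectives, opens with "A primary and secondary outcome was defined as the primary goal" and then describes both displacement and VAS well-being. Section 5.1 repeats the sentence but describes displacement only: "The primary outcome, the displacement of the patella, detected by an imaging ultrasound device". Section 5.2 lists the VAS: "The secondary outcome, the recording of the subjective well-being of the test person, is determined using a visual analogue scale".

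Section 10.1 gives each outcome its own pair of hypotheses. For displacement: "H1 The patella shifts significantly more during repetitive mobilizations than during a single mobilization by the patello". For the VAS: "H1 Subjective well-being changes significantly more with repetitive mobilizations than with a single mobilization by the patello". The time factor has six levels: pre-mobilization, then 1, 10, 20, 30 and 50 mobilizations.

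Section 10.3.2 holds the only efficacy analysis: "Repeated measures analysis of variance (MANOVA) A 2-factor analysis is performed", with "The significance level is set at $P < 0.05$, and the statistical data analysis is carried out with SPSS V. 24". It names no outcome. Section 10.3.3 provides no secondary analysis. Chapter 10 contains no testing order, alpha split, multiplicity adjustment or named contrast.

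**The concern.** The labels rank the two outcomes, but the analysis chapter does not turn that ranking into a testing rule. The VAS hypothesis is parallel to the displacement hypothesis. With no secondary analysis in 10.3.3, it is either tested inside the primary analysis or not at all.

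The second gap is the contrast. Both hypotheses compare repetitive with single mobilization. An overall test of a six-level time factor that includes the pre-mobilization reading does not answer that: it could be significant merely because the first mobilization moves the patella. Some contrast against reading 2 is needed, and there are four repetitive readings to choose from. Sections 4.3 and 9.2.4 also look for lasting or cumulative effects over two measurement days, yet day is not a factor in 10.3.2.

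At stake is whether a significant result on a 10.1 hypothesis can be read at the stated 5%. If outcome or contrast is chosen after the data are seen, it cannot.

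**Working it through.** **Inputs.** n = 30, effect size 0.68 and power 0.95 (synopsis, number of participants); significance level 0.05, sidedness not stated (10.3.2 and synopsis); two outcomes, each with a hypothesis (10.1); four repetitive levels against one single-mobilization level (10.1); no interim analyses (10.3.4).

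**1. The plan's own figure.** The synopsis does not say which outcome, test or alpha its power calculation used. Take one paired comparison with standardised difference d = 0.68: the noncentrality is d × √n = 0.68 × √30 = 3.72 on 29 degrees of freedom.

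- Two-sided 0.05: power 0.949; detectable d at 95% power 0.681. This matches.
- One-sided 0.05: power 0.977; detectable d 0.615. No match.

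So the figure fits a single paired test at two-sided 0.05, with no allowance for a second outcome or for several contrasts.

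**2. Displacement decides, one test.** The error is 5%.

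**3. Two outcomes tested separately, a claim allowed on either, both nulls true.** If independent: 1 − (1 − 0.05)² = 1 − 0.9025 = 9.75%. Ceiling for any dependence: 0.05 + 0.05 = 10%. With bivariate normal test statistics:

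| Correlation | Chance of at least one false positive |
|---|---|
| 0 | 9.75% |
| 0.3 | 9.5% |
| 0.5 | 9.1% |
| 0.7 | 8.3% |
| 0.9 | 7.0% |

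**4. Each repetitive level compared with reading 2, unadjusted, one outcome, one day.** Four independent tests would give 1 − 0.95⁴ = 18.5%. The four differences share reading 2, so they are correlated (0.5 when readings are independent). Simulation with n = 30, equal true means, normal readings, two-sided paired t-tests and 40,000 runs gives about 16%. Serial correlation between successive readings lowers this: about 15% at 0.5 and about 14% at 0.8.

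**5. Two remedies compared.**

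- Equal split, 0.025 per outcome: error 1 − 0.975² = 4.94% if independent, but power at d = 0.68 falls from 0.949 to 0.906.
- Fixed sequence, displacement then VAS, each at 0.05: if the displacement null is true, any false claim requires first rejecting it, at most 5%. If it is false, only the VAS test can err, again at most 5%. The displacement test keeps the full 0.05, so its power is unchanged.

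**The case against.** The strongest reply is that the outcomes are already ranked. The sentence in 4.2 and 5.1 itself speaks of one primary and one secondary outcome, and the synopsis, the overview, 4.2, 5.1, 5.2 and 9.1.1 all label displacement primary and the VAS secondary. The overview and section 3.5 tie proof of effectiveness to the patella being moved, not to well-being, and the VAS hypothesis states no direction of benefit. Section 9.4 describes the study as focused on basic findings. On this view, formal gatekeeping is more than a 30-volunteer, single-group study needs.

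Most of this stands. A reader might infer that the outcomes are co-primary and that the trial can claim effectiveness on either one, with an error rate of about 10%. The documents do not support that: they contain no either-outcome success rule, and they do not say whether the analysis is run per outcome or jointly. A joint test would hold the global error at 5%, although it would not answer the two 10.1 hypotheses separately. Nor is a false positive on a 10.1 hypothesis automatically a false claim that the device works, because those hypotheses concern repetition and not whether the patella moves at all.

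A reader might also multiply the level comparisons over both outcomes and both days and reach about 50%. That would be 16 unadjusted tests which no section plans, and it should carry no weight.

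What the reply does not remove is the missing contrast. Even with displacement as the sole deciding outcome, its 10.1 hypothesis has no single specified test.

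**Conclusion.** The point holds as a cheap improvement, not as a demonstrated inflation of the trial's error rate. The plan mixes two outcomes in its primary goal and tests repetitive against single mobilization without an order, an adjustment or a named contrast.

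The size depends on how the gap is filled: 5% with one displacement test; 7.0% to 9.75% over the correlations examined, and never above 10%, if either outcome could support a claim through separate tests; about 14% to 16% for one outcome on one day if all four levels are compared at 0.05. The last two cases assume true nulls throughout and an analysis that the plan leaves open but does not prescribe. The last also assumes normal readings, with serial correlation between 0 and 0.8.

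**What to change.** - **4.2 and 5.1:** state that displacement alone is the primary outcome, and move the VAS paragraph of 4.2 to the secondary objectives in 4.3. Deleting a word from the opening sentence is not enough, because the VAS text would still sit under the primary objectives.
- **10.3.2, contrast:** pre-specify one contrast for repetitive versus single mobilization, for example the mean of readings 3 to 6 minus reading 2, taken over both days. Say how it is formed when an interval or day is missing, since 10.2 and 10.4 keep partial data.
- **10.3.2, order:** test that contrast for displacement first at two-sided 0.05. Test the same contrast for the VAS at 0.05 only if displacement is significant.
- **10.3.2, other comparisons:** Holm-adjust level-by-level or day-by-day comparisons within each outcome, or report them as estimates with 95% confidence intervals and no claim.

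The cost is wording only, with no extra subjects or measurements. The synopsis power figure carries over if its 0.68 is a standardised difference on the named contrast, which the sponsor should confirm. The downside is that no confirmatory VAS claim is possible if displacement is not significant.

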4.3 Secondary Objectives

Multiple measurements will be performed to detect a possible sustained and/or cumulative effect of patellar mobilization. The measurements are repeated 2x per week in the same week, with a break of at least 2 days, as described in chapter 4.2.

4.4 Other safety aspects (long-term)

No short-term risks are to be expected from this study other than those discussed so far (see 3.7 Risks / Benefits).

5 STUDY OUTCOMES

5.1 Primary outcomes

A primary and secondary outcome was defined as the primary goal. The primary outcome, the displacement of the patella, detected by an imaging ultrasound device (esaote MyLabClassicC, Genoa, Italy, www.esaote.com) and evaluated by a dedicated software (OsiriX, www.osirix-viewer.com), is represented in mm and is considered an objective parameter.

5.2 Secondary outcomes

Subjective information on general well-being

The secondary outcome, the recording of the subjective well-being of the test person, is determined using a visual analogue scale (VAS scale 0 - 10) and reflected in the number of cm. The value "0" describes "maximum feeling of well-being", the value "10" a "maximum feeling of discomfort". The value is considered a subjective parameter.

Security considerations

SUPSI

No further results are recorded that would serve safety.

Discontinuation of the experiment is the responsibility of the examiner with regard to the subject's subjective feelings and expressions.

If a test subject does not feel comfortable during the intervention according to his or her subjective assessments, he or she can discontinue the experiment and withdraw participation in the study without any disadvantages.

6 STUDY DESIGN

Study design and justification

This clinical effectiveness study investigates the effect of apparatus-based, passive mobilization of the patella. The group size is $n = 30$.

Table 2: Study design

Time	Preparation	Pre	1 Mob.	10 Mob.	20 Mob.	30 Mob.	50 Mob.
Time (min)		5	10	20	30	40	50
Measurement		1.	2.	3.	4.	5.	6.
Subject information	X						
Consent	X						
Demographics	X						
Intervention			X	X	X	X	X
Ultrasound image		X	X	X	X	X	X
Subj. Well-being		X	X	X	X	X	X

6.1 Method for minimizing influencing factors

6.1.1 Randomization

Randomization is used to randomly determine the application side, left or right knee.

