Background and Rationale:	Restricted movement of the knee joint hinders the everyday life of the affected person. They can be caused by osteoarthritis or after surgical procedures on the knee joint. The therapy of choice for limited knee mobility is the active and passive mobilization of the knee joint (Art. Genu, Art. Patellofemorale, Art. Tibiofibulare) with involvement of the soft tissue mantle (muscles, connective tissue). Active mobilization is carried out by the patient independently through a specific exercise program. Passive mobilisation is part of physiotherapeutic treatment. The aim of mobilisation is to activate the formation of synovial fluid, to regulate the tone of the muscles and to influence the fibre alignment of the collagen tissue. The Patello device was built to perform passive, continuous mobilization of the patella as part of rehabilitation with limited knee mobility. The area of application and indication is based on the widely used "Kinetec" knee and hip mobilisation splint. What is innovative about the Patello is that only the Art. patellofemoral is mobilized; the patella is moved on its plain bearing in the cranial and caudal directions.
Objective(s):	The aim of this clinical trial is to prove the effectiveness of the patello.
Outcome(s):	Primary outcome: Objectification of the displacement of the patella to cranial and caudal measurement with an imaging ultrasound device (esaote MyLabClassicC, Genoa, Italy, www.esaote.com). Secondary outcome: Subjective well-being of the subject measured by a visual analogue scale (VAS scale 0 - 10). The knee to be tested is determined by lot (randomized) per test person. The outcomes are recorded after 1, after 10, after 20, after 30 and after 50 mobilizations in the caudal deposition position. The entire measurement procedure is carried out 2x in a week per test subject with a 2-day break in between.
Study design:	Clinical effectiveness study

SUPSI

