	
Examiner
 
- [name]^{1,2}- [name], Drs.^{1,2}- [name], MSc¹- [name] 
¹ University of Applied Sciences and Arts Southern Switzerland SUPSI, Department of Business Economics, Health and Social Care, Physiotherapy Graubünden, [name]
 
² THIM University of Applied Sciences in Physiotherapy, [name]
 
³ Medical Center Bad Ragaz, [name]

Investigator(s):	
Contact / Director of Studies
 
[name], PhD
 
University of Applied Sciences and Arts Southern Switzerland (SUPSI) Department of Business Economics, Health and Social Care Physiotherapy Graubünden [name] [contact] [contact]

Study Centre(s):	Single Centre Study: Rehabilitation Research Laboratory University of Applied Sciences and Arts Southern Switzerland SUPSI Department of Business Economics, Health and Social Care Physiotherapy Graubünden [name]
Statistical Considerations:	
Patellar displacement during mobilization application by the patello. Repeated measures analysis of variance (MANOVA)
 
A 2-factor analysis is carried out.
 
Factor 1: Intervention Patello
 
Factor 2: Time intervention: Start (pre-intervention, 1st measurement), after a single mobilization (2nd measurement), after 10 (3rd measurement), after 20 (4th measurement), after 30 (5th measurement), after 50 mobilizations (6th measurement).
 
The significance level is set at $P < 0.05$, and distatistical data analysis is carried out using the Statistical Package for Social Sciences (SPSS V. 24) from IBM, New York, USA.

SUPSI

GCP Statement:	This study will be conducted in compliance with the protocol presented here, the current version of the Declaration of Helsinki, the ICH-GCP, ISO EN 14155 (where applicable), and the Swiss Human Research Ordinance HFV.
-----------------------	--

SUPSI

Overview of the study

Knee joint mobility can be limited by arthritic or post-operative functional or structural changes. Reduced knee joint mobility can interfere with the affected person's everyday activities. Active movement of the knee promotes the formation of synovial fluid, which is essential for the supply of cartilage tissue. Passive mobilization techniques as part of a physiotherapeutic treatment release structural blockages and favor the fiber alignment of the collagen tissue.

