7.3 Group assignment

SUPSI

There will be no group assignment.

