7.4 Discontinuation of study participation

If a participant withdraws from the study before the measurements have begun, the allocation lot is returned to the pot in a new envelope and a new participant is sought.

If a participant is eliminated during the measurements, all data collected up to that point will be evaluated as far as possible and included in the data analysis (in accordance with Art. 9 ClinO). In this case, no new participant will be recruited to collect the missing records.

The data will be stored encrypted with a code during the study period and evaluation of the data.

The conditions for the termination of the experiment were described in chap. 5.4.

Participants are not disadvantaged by discontinuing their participation in the study.

SUPSI

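### Application side is drawn by lot but used in no planned analysis or summary; adding it would be a small, nearly free gain in precision

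*Combined protocol and SAP*

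**What the plan says.** The synopsis states that "The knee to be tested is determined by lot (randomized) per test person", so each subject contributes one knee and side is a between-subject characteristic. Section 6.1.1, under the heading on minimising influencing factors, repeats this: "Randomization is used to randomly determine the application side, left or right knee". Nothing else is randomised. Section 7.3 says "There will be no group assignment", and sections 8.1.2 and 8.2.2 state that there is no control intervention.

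The left:right ratio is not given. Section 7.4 only shows that lots come from a pot: if a subject withdraws before measurement, "the allocation lot is returned to the pot in a new envelope and a new participant is sought".

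The primary analysis (10.3.2) reads "Repeated measures analysis of variance (MANOVA) A 2-factor analysis is performed". The synopsis gives the first factor as "Factor 1: Intervention Patello". The second factor is time, with six levels from the pre-intervention reading to the reading after 50 mobilisations. Section 10.1 names the same two factors. Section 10.3.3 has no secondary analysis. Side is not mentioned in chapter 10 as a factor, covariate, subgroup or line in a table.

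**The concern.** In a one-group study a left/right draw has no second arm to balance. It keeps the subject or examiner from picking the convenient knee, but it does not remove a side effect, which could arise for example from leg dominance, device fit or probe access. It turns that effect into variation between subjects, and only a side term in the analysis takes the variation out again. The protocol identifies side as an influence to be controlled and then does not carry it into the analysis.

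At stake is some precision in the time contrasts, and a simple description of whether displacement looks similar on left and right knees. The validity of the primary test is not at stake.

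**Working it through.** **Inputs.** From the documents: n = 30, effect size 0.68 and power 0.95 (synopsis); significance level 0.05 (10.3.2); H1 compares repetitive with single mobilisation (10.1). Assumed, because the documents give no figure: a pot of 15 left and 15 right lots; side differences of 0.5, 1 or 2 SD, where SD is that of the within-subject contrast among subjects tested on the same side.

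**1. The plan's own figure.** The synopsis does not name the test behind 0.68. A two-sided paired t-test with n = 30 and alpha 0.05 gives a detectable standardised difference of 0.681 at power 0.95, and power 0.949 at 0.68. The stated figure is therefore reproduced as a within-subject comparison. A one-sided test (0.615) and a six-level repeated-measures F-test (f = 0.34 or 0.24, for correlation 0 or 0.5) do not match.

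**2. What cancels.** Write the reading of subject i at measurement j as

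y_ij = m_j + a_i + b·s_i + g_j·s_i + e_ij, with s_i = +1/2 or −1/2 for side.

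- H1 contrast, taken as the mean of measurements 3–6 minus measurement 2: a_i and b·s_i drop out. What remains of side is (mean of g_3 to g_6 − g_2)·s_i.
- Suppose one side moves further by a constant amount D at every measurement from the 2nd to the 6th. Then g_1 = 0 and g_2 = … = g_6 = D. The H1 contrast receives (D − D)·s_i = 0.
- The pre-versus-post contrast, y_ij − y_i1, receives D·s_i. Because the pre reading is a level of Time, this Side x Time term also enters the error of the overall Time test.

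Simulation agrees: with a constant side difference of 0, 1 or 2 between-subject SD, power of the paired contrast stays at about 0.95 and the SD of the change stays at 1.00.

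**3. Cost of a Side x Time difference with a 15:15 pot.** Let the contrast differ by g SD between sides. The between-side sum of squares has expectation (15 × 15 / 30)·g² + 1 = 7.5g² + 1, and the within-side sum of squares has expectation 28. Ignoring side, the expected variance estimate is (28 + 1 + 7.5g²)/29 = 1 + 7.5g²/29. The ratio of CI widths, ignoring side over including it, is about √(1 + 7.5g²/29) × 2.045/2.048.

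- g = 0.5: √1.0647 × 0.9985 = 1.030, so 3% too wide.
- g = 1: √1.2586 × 0.9985 = 1.120, so 12% too wide.

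Simulated results:

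| Side difference in the contrast | Coverage ignoring side | Power at 0.68 ignoring side | Power at 0.68 with side |
|---|---|---|---|
| 0 | 95.0% | 0.949 | 0.948 |
| 0.5 SD | about 95.7% | 0.942 | 0.948 |
| 1 SD | about 97.1% | 0.917 | 0.948 |
| 2 SD | not used here | 0.782 | 0.948 |

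Coverage above 95% means the test is conservative, not anti-conservative.

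**4. Fair independent draw instead of a fixed pot.** The side split is now random, and its variation belongs in the standard error. Simulated coverage ignoring side is 95.0% at both 0.5 and 1 SD. The variance of the mean is (1 + g²/4)/30, so the standard error is √1.0625 = 1.031 or √1.25 = 1.118 times its value without a side difference. Precision is lost, but the interval is correctly calibrated. A split of 20:10 or worse has probability 9.9%.

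**5. Cost of including side.** With 15:15 and no side difference, error degrees of freedom go from 29 to 28, power at 0.68 from 0.9494 to 0.9489, and the simulated CI width rises by 0.14%. This low cost depends on the balance. At 20:10 the equally weighted mean has standard error 0.5 × √(1/20 + 1/10) = 0.194, against √(1/30) = 0.183, about 6% more.

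**6. What a side comparison could show.** With 15 per side, the smallest detectable difference is d = 1.06 at 80% power and 1.36 at 95%.

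**The case against.** The strongest objection is that the primary hypothesis compares the same knee with itself. A reader might infer from the missing side term that every left/right difference in displacement sits in the error. The documents do not support that: for H1, a difference that is constant over measurements 2 to 6 cancels. This part of the objection stands. It does not reach the whole plan, because the pre reading is a level of Time and the stated aim is to show that the device moves the patella. The documents also do not say whether raw position or displacement from the pre reading is analysed.

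A reader might also infer that the interval is too wide whenever the sides differ. That requires a fixed split, which the pot in 7.4 suggests but does not establish. Under a fair independent draw, coverage is 95%, and a lean towards one side is ordinary sampling variation already in the standard error.

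Three further points are fair. The size of any side difference is assumed. Subjects are healthy adults aged 18 to 30, and pressure is set to individual tolerance, so the difference may be small. The draw is also not pointless without a side term, since it prevents selection of the easier knee. Finally, comparing sides is not a study objective, so the plan should not be faulted for leaving that question unanswered, and the documents do not rule out a summary by side. What remains is that data already held could improve precision at almost no cost and are not used.

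**Conclusion.** The gap is real but minor. Side is the only randomised element, and no planned analysis or summary uses it. If the sides differ in the change over mobilisations, or in displacement from the pre reading, the difference adds to the error and costs precision. With an assumed 15:15 pot the CI is about 3% too wide at 0.5 SD and 12% at 1 SD, and power at 0.68 is 0.94 or 0.92 instead of 0.95.

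It would be wrong to conclude that the primary test is biased or its type I error inflated. Neither follows under a fixed pot or a fair draw. All sizes rest on assumed side differences. The plan also states no confidence interval, only a significance level, so the width figures describe the interval that would accompany the test.

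Separately, and more seriously, the Intervention factor has a single level because there is no control. The two-factor model therefore has to be rewritten in any case, and side is the between-subject factor that the design does contain.

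**What to change.** - **6.1.1:** state that the pot holds 15 left and 15 right lots. The rule in 7.4 for returning a lot after withdrawal before measurement fits this.
- **10.1 and 10.3.2:** add application side as a between-subject factor, with Side x Time, and estimate the time effects with the two sides weighted equally.
- **Reporting:** give mean displacement by side and the Side x Time estimate with 95% CI, labelled descriptive, because 15 per side detects only large differences (d about 1.06 at 80% power).

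The cost is one error degree of freedom, about 0.14% in CI width with a 15:15 split, and a few words in the protocol. No new data are needed, since the side is known from the lot. Subjects lost during the measurements are not replaced, so the analysed split may drift from 15:15, and the cost rises with the imbalance. Priority: minor, optional improvement.
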